4.8. Treatment After the End of Study

After the Safety Period, patients will have their taper schedule initiated over a 3-6 day period (see Section 3.1.2).

5. STUDY DRUG MATERIALS AND MANAGEMENT

5.1. Labeling and Packaging

5.1.1. Labeling

The labels for the investigational product will contain all information according to regulatory requirements.

5.1.2. Packaging

The investigational product will be supplied in 30 mL containers of a 100 mg/mL strength (i.e., 3000 mg per container).

Non-proprietary or common name of drug product	Cannabidiol Oral Solution, 100 mg/mL
Dosage form	Oral solution
Strength	100 mg/mL

Please refer to the Cannabidiol Oral Solution IB for additional information on the drug formulation.

The investigational product will be clearly marked according to FDA and/or ICH requirements regarding use for clinical study investigation only and will be labeled with the investigational product name, study reference number, storage conditions, and expiry date. It is the responsibility of the investigator to ensure that accurate accountability records are maintained throughout the study. Study center staff will dispense the investigational product according to the handling instructions.

5.2. Dispensing and Storage

IP will be stored at controlled room temperature (20 to 25 degrees Celsius, 68 to 77 degrees Fahrenheit) at the study centers.

Cannabis and its constituents (including CBD) are Schedule I controlled substances and subject to all applicable local and federal laws and regulations regarding these products. This includes security provisions for storing the controlled substances and for dispensing in a manner to prevent diversion. Additionally, the Sponsor or investigator must provide a statement of the quantity to be manufactured and the sources of the chemicals to be used or the substance.

The DEA regulations detail specific security requirements for storage of the investigational product. Licensed practitioners must store controlled substances in a "securely locked, substantially constructed cabinet" and must notify the DEA of the theft or significant loss of any controlled substances within one business day of discovering such loss or theft. Furthermore, all practitioners are prohibited from hiring employees who have been convicted of a drug-related felony or who have had a DEA registration denied or revoked.

Investigators are responsible for ensuring that all applicable licensures are in place and storage conditions are appropriate.

Doses of Cannabidiol Oral Solution will be administered from the Schedule I-licensed study center.

The study centers are required to provide complete information, including case report forms (CRFs) and final outcomes, on all instances of addiction, abuse, misuse, overdose, drug diversion/drug accountability, discrepancies in amount of the clinical supplies of the investigational product, noncompliance, protocol violations, lack of efficacy, individuals lost to follow-up, and any other reasons why patients dropped out of the study.

5.3. Drug Supply and Accountability

The investigator, a member of the investigational staff, or a hospital pharmacist must maintain an adequate record of the receipt and distribution of all study medication using the Drug Accountability Form. These forms must be available for inspection at any time.

All supplies of Cannabidiol Oral Solution should be accounted for at the termination of the study and a written explanation provided for discrepancies. All unused supplies and packaging materials are to be inventoried and returned to the Sponsor or a designee by the investigator. The investigator is not permitted to return or destroy unused clinical drug supplies or packaging materials unless authorized by the Sponsor or a designee.

If the study is terminated, discontinued, suspended, or completed, all unused supplies of the investigational product may be destroyed via the use of a third-party vendor or be returned to the Sponsor or a designee after the final drug accountability check has been performed. A certificate of destruction will be provided to the Sponsor.

All regulations issued by the DEA concerning the accountability of Schedule I medications will be followed (e.g., prevention of diversion).

6. STUDY ASSESSMENTS

6.1. Safety Assessments

For all patients physical examination, vital signs (seated blood pressure, pulse rate, temperature, and respiration rate), clinical laboratory testing (hematology, chemistry, and urinalysis), 12-lead ECG, concomitant medication, C-SSRS, and AE assessments (including TEAEs and SAEs).

6.1.1. Physical Examinations

A physical examination (evaluation of general appearance, skin, eyes, ears, nose, throat, neck, lymph nodes, chest, heart, abdomen, and extremities) will be conducted for every patient during the Visit 1 (Day 1), all monthly and quarterly visits, and Visit 7 (End of Study) or Early Withdrawal.

6.1.2. Vital Signs

Vital signs (seated blood pressure, pulse rate, temperature and respiration rate) will be measured during Visit 1 (Day 1), all monthly & quarterly visits, and Visit 7 (End of Study) or Early Withdrawal. Additional vital sign measurements may be performed as deemed medically necessary by research personnel.

6.1.3. Electrocardiograms

A resting 12-lead ECG will be conducted during Visit 1 (Day 1), all monthly & quarterly visits, and Visit 7 (End of Study) or Early Withdrawal.

6.1.4. Clinical Laboratory Assessments

Blood samples for hematology and chemistry assessments and urine sample for urinalysis will be collected during Visit 1 (Day 1), all monthly & quarterly visits, and Visit 7 (End of Study) or Early Withdrawal.

- Hematology: hemoglobin, hematocrit, total and differential leukocyte count, red blood cell (RBC), and platelet count.
- Chemistry: albumin, blood urea nitrogen (BUN), creatinine, total bilirubin, alkaline phosphatase (ALP), aspartate transaminase (AST), alanine transaminase (ALT), sodium (Na⁺), potassium (K⁺), chloride (Cl⁻), lactate dehydrogenase (LDH), uric acid, glucose, and calcium.
- Urinalysis (Visit 1 and Visit 7 or Early Withdrawal only): pH, specific gravity, protein, glucose, ketones, bilirubin, blood, nitrite, leukocyte esterase, and urobilinogen. If protein, occult blood, nitrite, or leukocyte esterase values are out of range a microscopic examination will be performed.

A urine drug screen (amphetamines, barbiturates, benzodiazepines, cocaine, opiates, phencyclidine, and tetrahydrocannabinol) will be performed during at Visit 1 and Visit 7 (End of Study) or Early Withdrawal.

A urine dipstick pregnancy test will be performed on all female post-menarchal patients during at Visit 1 and Visit 7 (End of Study) or Early Withdrawal.

6.1.5. Columbia Suicide Severity Rating Scale (C-SSRS)

The C-SSRS is a prospective assessment tool routinely used in studies of drugs with any potential for CNS effects. It captures the occurrence, severity, and frequency of suicide-related thoughts and behaviors during the assessment period. The questionnaire will be completed during Visit 1 (Day 1) and at the end of the Safety Period (Visit 7) or Early Withdrawal Visit.

Patients who have significant findings for suicidal ideation as assessed by the C-SSRS must be referred to the investigator for follow-up evaluation.

6.1.6. Concomitant Medications

Will be assessed at all visits.

6.1.7. Adverse Events and Serious Adverse Events

6.1.7.1. Definition of Adverse Events

An AE is defined as any untoward medical occurrence in a patient administered a pharmaceutical product during the course of a clinical investigation. An AE can therefore be any unfavorable and unintended sign, symptom, or disease temporally associated with the use of an investigational product, whether or not thought to be related to the investigational product.

Patients will be monitored throughout the study for AEs. Monitoring for treatment-emergent AEs will begin as soon as the patient is dosed. All AEs must be followed until they are resolved or stabilized, or until all attempts to determine resolution of the event are exhausted. The investigator should use their discretion in ordering additional tests as necessary to monitor the progress of such events.

An AE may be:

- A new illness, not documented in the patient's s medical history;
- Worsening of a concomitant illness;
- An effect of the study medication; it could be an abnormal laboratory value, as well as a significant shift from baseline within normal range which the qualified investigator or medical qualified designate considers to be clinically important;
- A combination of two or more of these factors.

Surgical procedures themselves are not AEs. They are therapeutic measures for conditions that required surgery. The condition for which the surgery is required is an AE, if it occurs or is detected during the study period. Planned surgical measures permitted by the clinical study protocol and the conditions(s) leading to these measures are not AEs, if the condition(s) was (were) known before the start of study treatment. In the latter case, the condition should be reported as medical history.

Absence seizures will not be considered AEs. However, new seizure types and injury resulting from a seizure will be captured as AEs.

Patients will be monitored throughout the study for AEs. All AEs must be followed until they are resolved or stabilized, or until all attempts to determine resolution of the event are exhausted.

The investigator should use his/her discretion in ordering additional tests as necessary to monitor the progress of such events.

Adverse events reported prior to dose administration will be recorded as part of the patient's medical history.

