2. STUDY OBJECTIVE

The objective of this study is to assess the long-term safety and tolerability of Cannabidiol Oral Solution (CBD) in patients with Prader-Willi Syndrome.

Downloaded by PPD

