3.2.2. Exclusion Criteria

Patients will be excluded for any of the following:

- 1. Patient or parent(s)/caregiver(s) have daily commitments during the study duration that would interfere with attending all study visits.
- 2. Experienced an anoxic episode related to study drug requiring resuscitation during their previous study.
- 3. Uncontrolled Type I and Type II diabetes.

- 4. Developed an adverse event thought to be related to CBD in the previous study and for whom the Investigator determines that continuing treatment with CBD would not be in the best interest of the patient.
- 5. History of clinically significant gastrointestinal, renal, hepatic, neurologic, hematologic, endocrine, oncologic, pulmonary, immunologic, psychiatric, or cardiovascular disease, or other condition which would jeopardize safety or impact validity of results (per investigator).
- 6. Currently taking felbamate.
- 7. Compromised respiratory function or severe respiratory insufficiency.
- 8. Pregnant or lactating female.
- 9. In the opinion of the investigator, the patient is unsuitable in any other way to participate in this study.

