6.1.7.3. Causality/Drug Relationship Assessment

The relationship of the event to the study drug should be determined by the investigator according to the following criteria:

- Definitely related: The event follows a reasonable temporal sequence from the time of drug administration that cannot be explained, follows a known or expected response pattern to the study drug, that is confirmed by improvement on stopping and reappearance of the event on repeated exposure and that could not be reasonably explained by other factors such as the patient's clinical condition, intercurrent illness, or concomitant drugs.
- Not related: The event is most likely produced by other factors such as the patient's clinical condition, intercurrent illness, or concomitant drugs, and does not follow a known response pattern to the study drug, or the temporal relationship of the event to study drug administration makes a causal relationship unlikely.
- Possibly related: The event follows a reasonable temporal sequence from the time of drug administration, and/or follows a known response pattern to the study drug, but could have been produced by other factors such as the patient's clinical condition, intercurrent illness, or concomitant drugs.
- Unlikely related: The event follows little or no temporal sequence from the time of drug administration that makes a causal relationship improbable and/or other factors such as the patient's clinical condition, intercurrent illness, or concomitant drugs is a more likely alternative.
- Probably related: The event follows a reasonable temporal sequence from the time of drug administration, and/or follows a known response pattern to the study drug, and cannot be reasonably explained by other factors such as the patient's clinical condition, intercurrent illness, or concomitant drugs.

6.1.7.4. **Definition of Serious Adverse Events**

A serious AE (SAE) is any AE that fulfills any of the following criteria, as per 21 CFR 312.32:

- Results in death;
- Is life-threatening;
- Requires in-patient hospitalization or prolongation of existing hospitalization;
- Results in persistent or significant disability or incapacity;
- Is a congenital anomaly or birth defect;
- Is medically significant or requires intervention to prevent one of the outcomes listed above.

Serious AEs will be captured from the time of consent through the end of the study.

6.1.7.5. **Actions Taken**

Actions taken may consist of:

- None

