3.1 Safety Endpoints

The safety endpoints for this study are:

- Incidence, type and severity of adverse events (AEs) and serious adverse events (SAEs) associated with CBD, i.e. treatment emergent adverse events (TEAEs)
- Changes from baseline in vital signs, physical exam, ECG findings and laboratory values (hematology, chemistry and urinalysis)
- Change from baseline in weight

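### Protocol 6.1.7.1 excludes absence seizures from adverse events in a Prader-Willi safety study without giving a reason; recurrent or worsening cases go unrecorded and first cases are ambiguous

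*Protocol*

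**What the plan says.** Protocol 6.1.7.1 opens with a general definition: "An AE is defined as any untoward medical occurrence in a patient administered a pharmaceutical product during the course of a clinical investigation". Its list of what an AE may be includes "Worsening of a concomitant illness". Later in the section comes the exclusion, "Absence seizures will not be considered AEs", followed at once by "However, new seizure types and injury resulting from a seizure will be captured as AEs". No reason is given for either sentence.

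Protocol 6.1.7.4 makes seriousness depend on AE status: "A serious AE (SAE) is any AE that fulfills any of the following criteria, as per 21 CFR 312.32". Protocol 8.5.3.1 limits AE summaries to treatment-emergent events. SAP 6.7.2 codes the AEs recorded on the eCRF and has no seizure rule of its own.

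The sole objective in Protocol section 2 reads: "The objective of this study is to assess the long-term safety and tolerability of Cannabidiol Oral Solution (CBD) in patients with Prader-Willi Syndrome". The first safety endpoint in SAP 3.1 is "Incidence, type and severity of adverse events (AEs) and serious adverse events (SAEs) associated with CBD"; the list is not ranked.

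**The concern.** Leaving a seizure type out of AE recording can make sense where seizures are the disease under study and are counted by another instrument. Neither holds here. The indication is Prader-Willi Syndrome, the Schedule of Events has no seizure assessment, and neither document has a seizure endpoint. An excluded event is therefore not picked up elsewhere as an event.

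Two things are at stake. First, a study whose only objective is safety and tolerability would under-record one kind of neurological event. Second, two sites could treat the same first absence seizure differently, each with support in the text. An absence-seizure count of zero could then reflect the recording rule rather than the drug.

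**Working it through.** This is mainly a comparison of texts. The plan states no figure on this point to reproduce.

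**Step 1: apply the sentences to each case.**

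| Event | General definition (6.1.7.1) | Exclusion sentence | Sentence after it | Result |
|---|---|---|---|---|
| Recurrent absence seizure, no injury | AE if untoward | Not an AE | Does not apply | Not recorded |
| Worsening of existing absence seizures, no injury | AE (worsening of an illness) | Not an AE | Does not apply | Contradiction; lost if the exclusion is followed |
| First absence seizure in this patient | AE | Not an AE | AE, if it counts as a type new to the patient | Two readings |
| Injury from an absence seizure | AE | Not addressed (names the seizure only) | AE | Injury recorded |
| New seizure of another type | AE | Does not apply | AE | Recorded |

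**Step 2: follow an unrecorded event through the plan.**
- It is not a TEAE, so it is in no AE table (Protocol 8.5.3.1; SAP 6.7.2).
- Read literally, it cannot be an SAE, because an SAE must first be an AE (Protocol 6.1.7.4). The follow-up rules in 6.1.7.8 are also written for AEs and SAEs.
- Indirect traces may remain, such as a new concomitant medication or a withdrawal counted in disposition, but not the event itself.

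**Step 3: size.** The inputs are the maximum of 66 patients (Protocol 8.3, SAP 2.3) and the rule in SAP 6.7.2 that a patient counts once per category.
- Row for the preferred term: 1/66 = 1.5 percentage points per missed patient, if all 66 enroll.
- Any-TEAE incidence: no change if the patient has another TEAE; 1.5 points if not.
- Within a modal dose group of n patients, the row moves by 100/n points. Group sizes are not known in advance, because the groups are formed from the doses actually taken.

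**Step 4: what an observed zero would mean.** The documents give no rate of absence seizures in this population, so the rates p below are assumptions. If all absence seizures were recorded in 66 patients, the chance of at least one affected patient is 1 − (1 − p)^66:

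| Assumed true rate | Chance of at least one affected patient |
|---|---|
| 0.5% | 28% |
| 1% | 48% |
| 2% | 74% |
| 3% | 87% |
| 5% | 97% |

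A genuine 0/66 would give a one-sided 95% upper bound of 1 − 0.05^(1/66) = 4.4%. If the exclusion is applied as absolute, the count is zero by definition and supports no bound.

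**The case against.** The strongest reply is that a specific exception to a general definition is ordinary drafting. The same section also exempts surgical procedures. Read in order, the sentence beginning with the contrast is an exception to the exclusion, so a first absence seizure is captured as new for that patient. Exclusion criterion 5 may also keep out many patients with a relevant neurologic history, so few events would be affected.

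Part of this stands. A reader might infer that a whole class of neurological events is removed. The documents do not support that: new seizure types, seizure injuries and all non-seizure neurological events remain reportable. The affected group may well be small.

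The rest does not stand. The surgical exemption says where the information goes instead: the underlying condition is recorded as an AE or as medical history. The seizure exemption names no such place and gives no reason. The favorable reading of the second sentence is possible but not stated, and it does nothing for recurrence or worsening. Criterion 5 rests on the investigator's judgment, so a patient with absence seizures can still be enrolled.

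**Conclusion.** The point holds in a limited form and should be corrected. Followed as written, 6.1.7.1 loses recurrent or worsening absence seizures without injury, conflicts with its own AE definition on worsening, and leaves first absence seizures open to two readings. The number of patients affected cannot be derived from the documents and is probably small. The 1.5 points per missed patient assumes that all 66 enroll and applies to the preferred-term row.

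Three further inferences are tempting but not supported:
- **That the primary endpoint is affected.** AE and SAE incidence is listed first among the safety endpoints, but neither document labels any endpoint primary, and the safety analysis is descriptive.
- **That the sentence was carried over from the sponsor's epilepsy trials.** This is plausible given the seizure-disorder program in Protocol 1.3, but those protocols are not available. Protocol 1.3.3 reports seizure among the most frequent AEs in the long-term seizure-disorder study. That does not show how absence seizures were handled, and it does not confirm the origin.
- **That each missed patient shifts overall AE incidence, or shifts a dose group of 22 by 4.5 points (1/22).** The first fails for any patient with another TEAE. The second assumes an equal three-way split that nothing in the documents supports.

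**What to change.** Delete or redraft both sentences together. The text should say that any new-onset or worsening seizure, absence seizures included, and any injury from a seizure is recorded under the general AE definition, and that a stable pre-existing seizure disorder is recorded as medical history. Deleting only the exclusion is not enough. The following sentence would lose what it refers back to and could be read as implying that other seizures are not captured.

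The change concerns event recording only. SAP 6.7.2 needs no new rule, because it codes whatever is recorded as an AE. The cost is a short protocol amendment, a note to sites and possibly a few more AE records.

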6.1.7.2. Classification of Adverse Events

Adverse events are to be recorded on the AE page of the patient's case report form (CRF). Severity will be graded according to the following definitions:

- Mild: The patient experiences awareness of symptoms but these are easily tolerated or managed without specific treatment.
- Moderate: The patient experiences discomfort enough to cause interference with usual activity, and/or the condition requires specific treatment.
- Severe: The patient is incapacitated with inability to work or do usual activity, and/or the event requires significant treatment measures.

6.1.7.3. Causality/Drug Relationship Assessment

The relationship of the event to the study drug should be determined by the investigator according to the following criteria:

- Definitely related: The event follows a reasonable temporal sequence from the time of drug administration that cannot be explained, follows a known or expected response pattern to the study drug, that is confirmed by improvement on stopping and reappearance of the event on repeated exposure and that could not be reasonably explained by other factors such as the patient's clinical condition, intercurrent illness, or concomitant drugs.
- Not related: The event is most likely produced by other factors such as the patient's clinical condition, intercurrent illness, or concomitant drugs, and does not follow a known response pattern to the study drug, or the temporal relationship of the event to study drug administration makes a causal relationship unlikely.
- Possibly related: The event follows a reasonable temporal sequence from the time of drug administration, and/or follows a known response pattern to the study drug, but could have been produced by other factors such as the patient's clinical condition, intercurrent illness, or concomitant drugs.
- Unlikely related: The event follows little or no temporal sequence from the time of drug administration that makes a causal relationship improbable and/or other factors such as the patient's clinical condition, intercurrent illness, or concomitant drugs is a more likely alternative.
- Probably related: The event follows a reasonable temporal sequence from the time of drug administration, and/or follows a known response pattern to the study drug, and cannot be reasonably explained by other factors such as the patient's clinical condition, intercurrent illness, or concomitant drugs.

6.1.7.4. **Definition of Serious Adverse Events**

A serious AE (SAE) is any AE that fulfills any of the following criteria, as per 21 CFR 312.32:

- Results in death;
- Is life-threatening;
- Requires in-patient hospitalization or prolongation of existing hospitalization;
- Results in persistent or significant disability or incapacity;
- Is a congenital anomaly or birth defect;
- Is medically significant or requires intervention to prevent one of the outcomes listed above.

Serious AEs will be captured from the time of consent through the end of the study.

6.1.7.5. **Actions Taken**

Actions taken may consist of:

- None
- Study drug discontinued
- Dose modified
- Required concomitant medication
- Required procedure
- Other

6.1.7.6. **Outcome at the Time of Last Observation**

The outcome at the time of last observation will be classified as:

- Recovered/resolved
- Recovered/resolved with sequelae
- Not recovered/not resolved
- Death
- Unknown

6.1.7.7. **Adverse Event Recording and Reporting**

Adverse events will be recorded throughout the study in the source documents and in the CRFs. The investigator will rate AEs for seriousness, intensity, causality, action taken, and outcome as described in the previous section.

Expedited reporting is required for serious unexpected adverse drug reactions. Fatal or life-threatening unexpected drug reactions must be reported by the Sponsor to regulatory agencies no more than 7 days after the Sponsor's first knowledge of the reaction; followed by as complete a report as possible within 8 additional days. Unexpected drug reactions must be

reported no later than 15 days after the Sponsor's first knowledge of the reaction. In order to comply with these requirements, the investigator or delegate must inform the Sponsor immediately upon occurrence of any SAE. The site will complete the SAE Report Form as thoroughly as possible and e-mail it to Insys within 24 hours of the investigators first knowledge of the event.

Sponsor contact information is listed below:

Insys Development Company, Inc.

Email: [contact]

These SAE reports must contain the following information:

- A. Study name/number
- B. Study drug
- C. Investigator details (name, phone, fax, e-mail)
- D. Patient number
- E. Patient initials
- F. Patient demographics
- G. Clinical event
 - 1) Description
 - 2) Date of onset
 - 3) Treatment (drug, dose, dosage form)
 - 4) Adverse event relationship to study drug
 - 5) Action taken regarding study drug in direct relationship to the AE
- H. If the AE was fatal or life-threatening
- I. Cause of death (whether or not the death was related to study drug)
- J. Autopsy findings (if available)

The Sponsor or its representative will be responsible for notification to regulatory agencies.

